10.3.5. Reporting of SAEs

SAE Reporting to the Sponsor via an Electronic Data Collection Tool

- The primary mechanism for reporting an SAE to the Sponsor will be the electronic data collection tool.
- If the electronic system is unavailable, then the site will use the paper SAE data collection tool in order to report the event within 24 hours.
- The site will enter the SAE data into the electronic system as soon as it becomes available and within 24 hours of Investigator/site awareness.
- After the study is completed at a given site, the electronic data collection tool will be taken off-line to prevent the entry of new data or changes to existing data.
- If a site receives a report of a new SAE from a study participant or receives updated data on a previously reported SAE after the electronic data collection tool has been taken off-line, then the site can report this information on a paper SAE form (see next section) or to the study Medical Monitor (or designee) by telephone.

Prilenia Therapeutics

Study drug: Pridopidine
Protocol Number: PL101-HD301

- Contacts for SAE reporting are:
 - When the electronic system is not available please submit paper SAE forms to TFS Drug Safety at: [contact]

10.4. Appendix 4: Contraceptive Guidance and Collection of Pregnancy Information

10.4.1. Definitions

Woman of Childbearing Potential (WOCBP)

A woman is considered fertile following menarche and until becoming postmenopausal, unless permanently sterile (see below).

If fertility is unclear (e.g., amenorrhea in adolescents or athletes) and a menstrual cycle cannot be confirmed before the first dose of study drug, additional evaluation should be considered.

Women in the following categories are not considered WOCBP:

1. Premenarchal
2. Premenopausal female with 1 of the following:
 - Documented hysterectomy
 - Documented bilateral salpingectomy
 - Documented bilateral oophorectomy

For individuals with permanent infertility due to an alternate medical cause other than the above, (e.g., mullerian agenesis, androgen insensitivity), Investigator discretion should be applied to determining study entry.

Note: Documentation can come from the site personnel's review of the participant's medical records, medical examination, or medical history interview.

Postmenopausal female

- A postmenopausal state is defined as no menses for 12 months without an alternative medical cause.
 - A high follicle-stimulating hormone (FSH) level in the postmenopausal range may be used to confirm a postmenopausal state in women not using hormonal contraception or hormone replacement therapy (HRT). However, in the absence of 12 months of amenorrhea, confirmation with more than one FSH measurement is required. FSH may be repeated twice, separated by at least a month if the result of the first instance is more than 30 IU/L.
- Females on HRT and whose menopausal status is in doubt will be required to use one of the non-estrogen hormonal highly effective contraception methods if they wish to continue their HRT during the study. Otherwise, they must discontinue HRT to allow confirmation of postmenopausal status before study enrollment.

10.4.2. Contraception Guidance

Male Participants

Male participants are eligible to participate if they agree to the following from informed consent through 90 days after the last dose of study drug:

- Refrain from donating sperm, except for the purpose of fertility analysis as part of this protocol

PLUS, either:

- Be abstinent from heterosexual intercourse as their preferred and usual lifestyle (abstinent on a long-term and persistent basis) and agree to remain abstinent

OR

- Must agree to use contraception/barrier (a male condom)

Female Participants

- A female participant is eligible to participate if she is not pregnant or breastfeeding, and at least one of the following conditions applies:
 - Is not a WOCBP

OR

- Is a WOCBP and using a contraceptive method that is highly effective (with a failure rate of < 1% per year), preferably with low user dependency (see table below), from consent through 30 days after the last dose of study drug, and agrees not to donate eggs (ova, oocytes) for the purpose of reproduction during this period. The Investigator should evaluate the effectiveness of the contraceptive method in relation to the first dose of study drug.
- A WOCBP must have a negative serum pregnancy test (minimum sensitivity 25 IU/L or equivalent units of β -HCG] at Screening and a negative urine pregnancy test before the first administration of study drug. During the Treatment period, urine pregnancy tests will be performed monthly. If the urine test is positive or cannot be confirmed as negative, a serum pregnancy test is required, and results must be negative.

Contraceptive use by men or women should be consistent with local regulations regarding the use of contraceptive methods for those participating in clinical studies.

Highly Effective Methods^a That Have Low User Dependency

- Implantable progestogen-only hormone contraception associated with inhibition of ovulation^b
- Intrauterine device (IUD)
- Intrauterine hormone-releasing system (IUS)^b
- Bilateral tubal occlusion
- Vasectomized partner

(Vasectomized partner is a highly effective contraceptive method provided that the partner is the sole sexual partner of the woman of childbearing potential and the absence of sperm has been confirmed. If not, an additional highly effective method of contraception should be used. Spermatogenesis cycle is approximately 90 days.)

Highly Effective Methods^a That Are User Dependent

- Combined (estrogen- and progestogen-containing) hormonal contraception associated with inhibition of ovulation
 - oral
 - intravaginal
 - transdermal
 - injectable
- Progestogen-only hormone contraception associated with inhibition of ovulation^b
 - oral
 - injectable
- Sexual abstinence

(Sexual abstinence is considered a highly effective method only if defined as refraining from heterosexual intercourse during the entire period of risk associated with the investigational product. The reliability of sexual abstinence needs to be evaluated in relation to the duration of the study and the preferred and usual lifestyle of the participant.)

^a Failure rate of < 1% per year when used consistently and correctly. Typical use failure rates differ from those when used consistently and correctly.

^b If locally required, in accordance with Clinical Trial Facilitation Group (CTFG) guidelines, acceptable contraceptive methods are limited to those which inhibit ovulation as the primary mode of action.

Note: Periodic abstinence (calendar, symptothermal, post-ovulation methods), withdrawal (coitus interruptus), spermicides only, and lactational amenorrhoea method are not acceptable methods of contraception for this study. Male condom and female condom should not be used together (due to risk of failure with friction).

10.4.3. Collection of Pregnancy Information

Male participants with partners who become pregnant

- The Investigator will attempt to collect pregnancy information on any male participant's female partner who becomes pregnant while the male participant is in this study. This applies only to male participants who receive pridopidine.
- After obtaining the necessary signed informed consent from the pregnant female partner directly, the Investigator will record pregnancy information on the appropriate form and submit it to the Sponsor within 24 hours of learning of the partner's pregnancy. The female partner will also be followed to determine the outcome of the pregnancy. Information on the status of the mother and child will be forwarded to the Sponsor. Generally, the follow-up will be no longer than 6 to 8 weeks following the estimated delivery date. Any termination of the pregnancy will be reported regardless of fetal status (presence or absence of anomalies) or indication for the procedure.

Female participants who become pregnant

- The Investigator will collect pregnancy information on any female participant who becomes pregnant while participating in this study. The initial information will be recorded on the appropriate form and submitted to the Sponsor within 24 hours of learning of a participant's pregnancy.
- The participant will be followed to determine the outcome of the pregnancy. The Investigator will collect follow-up information on the participant and the neonate, and the information will be forwarded to the Sponsor. Generally, follow-up will not be required for longer than 6 to 8 weeks beyond the estimated delivery date. Any termination of pregnancy will be reported, regardless of fetal status (presence or absence of anomalies) or indication for the procedure.
- While pregnancy itself is not considered to be an AE or SAE, any pregnancy complication or elective termination of a pregnancy for medical reasons will be reported as an AE or SAE.
- A spontaneous abortion (occurring at <22 weeks gestational age) or still birth (occurring at >22 weeks gestational age) is always considered to be an SAE and will be reported as such.
- Any post-study pregnancy-related SAE considered reasonably related to the study drug by the Investigator will be reported to the Sponsor as described in Section 8.3.5. While the Investigator is not obligated to actively seek this information in former study participants, he or she may learn of an SAE through spontaneous reporting.
- Any female participant who becomes pregnant while participating in the study will discontinue study drug or be withdrawn from the study.

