For each participant, the last visit will be the Main Study EoS or Early Termination (ET) visit. For participants who stay on study drug and complete all scheduled visits during the double-blind study period, their EoS visit will be either Week 65 visit or Week 78. Participants who discontinue early from study drug will be encouraged to remain in the study and complete all other visits as scheduled for the full course of the study. Participants who withdraw from the study before Week 65 visit and are not willing to continue with the study visits and procedures for the full course of the study, will be asked to undergo an ET visit that will include evaluations as specified in the SoA ([Table 2 – Main Study](#)). Participants withdrawing from the Main Study will be encouraged to complete the same final evaluations as participants

⁷ If there is no need for genetic tests or washout from prohibited medication, the screening period should be completed within 3 weeks.

Prilenia Therapeutics

Study drug: Pridopidine
Protocol Number: PL101-HD301

completing the study according to this protocol (EoS visit of the Main Study), particularly safety and primary and secondary efficacy evaluations.

Eligible participants who complete the Main Study, 65- or 78-week double-blind Treatment period, will have the option to enroll into an OLE period, commencing at the Main Study EoS visit, and receive pridopidine. The OLE will consist of a 2-week Titration period and a Maintenance period. During the Titration period, participants will self-administer 1 capsule of pridopidine 45 mg PO, QD, in the morning for 2 weeks. Thereafter, pridopidine will be taken PO, bid, in the morning and in the afternoon (7-10 hours apart) until 12 months after the last participant completes the double-blind Treatment period.

Participants who are not continuing to the OLE study will be contacted by phone for a safety evaluation 2 weeks after the Main Study EoS/ET visit. AEs will be monitored for these 2 weeks until the safety telephone contact.

Throughout the study, participants will be assessed through on-site clinic visits, virtual visits (via telephone), and safety telephone calls (TCs), as specified in the corresponding SoAs ([Table 2](#) – Main Study, and [Table 3](#) – OLE) and study schemas ([Figure 1](#) – Main Study, and [Figure 2](#) – OLE).

[figure not shown]

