5.1. Inclusion Criteria – Main Study

Participants are eligible to be included in the study only if all of the following criteria apply:

Age

1. Twenty-five years of age (inclusive) and older, at the time of signing the informed consent.

Type of Participant and Disease Characteristics

2. Diagnosis of HD based on clinical features and the presence of ≥ 36 CAG repeats in the HTT, confirmed by historical laboratory quantified results or by a diagnostic test at Screening.
2. Diagnostic confidence level (DCL) of 4 (unequivocal motor signs, $\geq 99\%$ confidence) on the standardized motor exam UHDRS-TMS.
3. Adult-onset HD with onset of signs and symptoms ≥ 18 years of age.
4. Stage 1 or Stage 2 HD, defined as a UHDRS-TFC score of ≥ 7 , at Screening.
5. UHDRS-Independence Scale (IS) score $\leq 90\%$ at Screening.
6. UHDRS-TMS ≥ 20 at Screening.
7. Must meet all criteria required to move forward with the Randomization Authorization Flow (RAF) and be considered eligible by the RAF Reviewer.

Sex

8. Male or female.

Pregnancy and Contraception

Contraceptive use by men or women should be consistent with local regulations regarding the methods of contraception for those participating in clinical studies (refer to Appendix 4, Section 10.4).

9. Female participants of childbearing potential must have a negative β -human chorionic gonadotropin (β -HCG) test at Screening and Baseline, be sterile, or be postmenopausal.
10. Female participants of childbearing potential whose male partners are potentially fertile (i.e., no vasectomy) must use highly effective birth control methods stable for at least 3 months prior to Screening, for the duration of the study and for 30 days after discontinuation of the study drug.
11. Male participants must be sterile, or if they are potentially fertile/reproductively competent (not surgically [e.g., vasectomy] or congenitally sterile) and their female partners are of childbearing potential, they must use, together with their female partners, effective birth control methods for the duration of the study and for 90 days after study drug discontinuation.

Concomitant Therapy

12. For participants taking allowed antipsychotic, antidepressant, or other psychotropic medication, the dosing of medication as listed in Appendix 6 (Section 10.6), must be stable for at least 4 weeks before the Baseline visit, and throughout the study (unless clinically necessary to change).

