6.4. Measures to Minimize Bias: Randomization and Blinding

All participants will be centrally randomized on a 1:1 basis to receive either pridopidine or placebo using an Interactive Response Technology (IRT), based upon the stratification variables of whether they are HD1 or HD2 and whether they are taking neuroleptics or not.

All participants, site staff, Sponsor, CRO and vendors involved with the study will remain blinded to treatment assignments until the database is locked and the study unblinded. The CRO(s) creating the randomization assignments, implementing the IRT and drug packaging groups will follow their standard operating procedures to ensure no one, involved in the conduct of the study or review and analysis of data, is unblinded except as indicated below for emergency unblinding. Drug concentration information that would unblind the study will not be reported to investigative sites or blinded personnel until the study has been unblinded.

The IRT will be programmed with blind-breaking instructions. In case of an emergency, the Investigator has the sole responsibility for determining if unblinding of a participant's study drug assignment is warranted. Participant safety must always be the first consideration in making such a determination. If a participant's study drug assignment is unblinded, the Sponsor must be notified within 24 hours after breaking the blinding. The date and reason that the blinding was broken must be recorded in the source documentation and case report form, as applicable.

Appropriate personnel at the Sponsor or sponsor designee will unblind suspected unexpected serious adverse reactions (SUSARs) for the purpose of regulatory reporting. The Sponsor will submit SUSARs to regulatory agencies in blinded or unblinded fashion according to local law. The Sponsor will submit SUSARs to Investigators in a blinded fashion.

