8.3.5. Pregnancy

- Details of all pregnancies in female participants and female partners of male participants will be collected as outlined in Appendix 4 (Section 10.4).
- If pregnancy is reported, the Investigator should inform the Sponsor within 24 hours of learning of the pregnancy and should follow the procedures outlined in Appendix 4 (Section 10.4).
- Abnormal pregnancy outcomes (e.g., spontaneous abortion, fetal death, stillbirth, congenital anomalies, ectopic pregnancy) are considered SAEs.

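### Partner pregnancies are collected only for men on pridopidine, which blinded Main Study sites cannot identify, and required collection stops before the protocol's contraception periods end for participants dosed to their last visit

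*Protocol*

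**What the plan says.** Protocol 10.4.3 (Appendix 4) asks the investigator to try to collect information on any "female partner who becomes pregnant while the male participant is in this study", and then adds: "This applies only to male participants who receive pridopidine". The form is due at the sponsor within 24 hours of the site learning of the pregnancy. For female participants the same section collects pregnancies that begin during participation.

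Protocol 8.3.5 has no arm limit: "Details of all pregnancies in female participants and female partners of male participants will be collected". The same sentence then refers to Appendix 4 for how this is done.

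Protocol 6.4 says that participants, site staff and sponsor "will remain blinded to treatment assignments until the database is locked and the study unblinded". The investigator's only exception is emergency unblinding.

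The contraception periods are longer than the follow-up after dosing. Under 10.4.2, men must use a condom or abstain, and must not donate sperm, "from informed consent through 90 days after the last dose of study drug". Inclusion criterion 11 in 5.1 asks for "effective birth control methods for the duration of the study and for 90 days after study drug discontinuation". Women of childbearing potential have a 30-day period in both sections. The only text near a rationale for the 90 days is a remark under the vasectomized-partner method: "Spermatogenesis cycle is approximately 90 days".

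On last contact, Protocol 4.1 says that those not entering the open-label extension (OLE) "will be contacted by phone for a safety evaluation 2 weeks after the Main Study EoS/ET visit". Both schedules of activities place the final call 2 weeks after the End of Study or Early Termination visit (EoS/ET), with a window of ±5 days.

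**The concern.** Two rules in 10.4.3 do not fit the rest of the protocol.

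The first is the arm limit. Whether a partner pregnancy is reportable depends on the man's treatment, which the Main Study site may not know. The 24-hour deadline means that the decision cannot wait for database lock. A site that reads 8.3.5 will collect for every man. A site that reads 10.4.3 has a rule that it cannot apply. Different sites may settle this differently, so the pregnancy reports would reflect how each site read the text as well as what happened.

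The second is the time limit. The protocol asks men and women to take precautions for 90 and 30 days after the last dose, yet the duty to collect pregnancies ends with participation. Pregnancies should be few under mandatory contraception, so each report carries weight. A conception inside the precaution period but after the final call falls outside what 10.4.3 requires.

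**Working it through.** The plan gives no figure on this point to reproduce. The check is a comparison of passages and a count of days.

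**Arm limit**

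- 10.4.3 covers men who receive pridopidine; 8.3.5 covers all male participants.
- 8.3.5 defers to Appendix 4, and 10.4.3 is part of Appendix 4. Neither section says which governs.
- 6.4 withholds the treatment assignment, and a partner pregnancy is not listed as a reason to unblind.
- With 1:1 randomization, about half of the men in the Main Study fall outside 10.4.3.
- In the OLE everyone receives pridopidine (Protocol 2.3.2), so the limit excludes nobody there.

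**Time limit**

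Inputs:
- W, the contraception period after last dose: 90 days for men, 30 for women (5.1, 10.4.2).
- c, days from EoS/ET to the final call: 14, range 9 to 19 (4.1 and the schedules of activities).
- d, days from last dose to EoS/ET: 0 if dosed up to that visit. This is an assumption.
- Participation ends at EoS/ET or the last follow-up contact (SAP 5.5.7).

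Formula: uncovered days = max(0, W − (d + c)).

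Dosed to EoS/ET (d = 0):

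| Final call at day | Men | Women |
|---|---|---|
| 9 | 90 − 9 = 81 | 30 − 9 = 21 |
| 14 | 90 − 14 = 76 (76/90 = 84%) | 30 − 14 = 16 (16/30 = 53%) |
| 19 | 90 − 19 = 71 | 30 − 19 = 11 |

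With no follow-up call, the whole 90 or 30 days is uncovered. The same figures apply at the end of the OLE, where the call is also 2 weeks after the last visit.

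Men who stop drug early but stay in Main Study follow-up (call at day 14):

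- Stop at Week 72, EoS at Week 78: d + c = 6 × 7 + 14 = 56; gap 90 − 56 = 34 days.
- Stop at Week 58, EoS at Week 65: 7 × 7 + 14 = 63; gap 27 days.
- Stop at Week 52, EoS at Week 65: 13 × 7 + 14 = 105; gap 0.

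The gap closes once the last dose is at least 90 − 14 = 76 days before EoS for men, or 30 − 14 = 16 days for women. In the OLE, a participant who stops drug is withdrawn (Protocol 7.2), so continued follow-up off drug does not close it.

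**The case against.** The strongest reply is that a site has a workable course without touching the blind: follow 8.3.5 and collect for every man. That stands. A reader might infer that 10.4.3 forces a site to unblind, but no passage tells it to. The defect is that 10.4.3 contradicts the workable course.

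A second reply is that late pregnancies are not lost. Section 8.3.5 states no end date, asks for any reported pregnancy to reach the sponsor within 24 hours, and classes abnormal outcomes as serious adverse events. Section 8.3.1 requires notice of a related serious event learned of after participation. This stands in part. It rules out saying that such pregnancies are never collected, but it creates no duty to seek them. Section 8.3.5 defers to Appendix 4, 8.3.1 disclaims active search, and the post-study sentence in 10.4.3 sits under female participants and relies on spontaneous reports.

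A third reply is that the 30 and 90 days are precaution periods. The protocol does not call them exposure windows or promise data to support them. The SAP plans no comparison of pregnancies by arm, only a listing of pregnancy test results (SAP 8.10). This also stands: the loss of a placebo comparison of very few events is a weak harm. The case rests on consistent and complete safety reporting.

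**Conclusion.** The point holds as a conflict in the wording and a gap in required safety collection. The arm limit in 10.4.3 cannot be applied by blinded sites in the Main Study and contradicts 8.3.5. Separately, about 76 of 90 days for men (71 to 81) and 16 of 30 for women (11 to 21) lie beyond required collection.

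Those day counts assume dosing up to EoS/ET, either in the Main Study without OLE entry or at the end of the OLE, and a final call in its window. A reader might take 76 days as general. It is not: the gap shrinks, and can vanish, for those who stop drug early and remain in Main Study follow-up. Nor are half of all partners excluded throughout the study, because that share applies only to the double-blind Main Study.

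The matter concerns safety data only. The primary endpoint, alpha and power are untouched.

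**What to change.** 1. Delete the sentence in 10.4.3 that limits collection to men receiving pridopidine, so that the section agrees with 8.3.5 and with the blinding in 6.4.
2. Restate the collection period in 10.4.3, for both sexes, as: during study participation, or through 30 days (female participants) or 90 days (partners of male participants) after the last dose, whichever is later.
3. At the final safety call, remind participants to report pregnancies in that period.

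The phrase *whichever is later* matters. A period counted only from the last dose would shorten coverage for those who stop drug and stay in the study. A woman who stops at Week 26 and stays through Week 78 and the final call is now covered for (78 − 26) × 7 + 14 = 378 days after her last dose, and a plain 30-day rule would cut that to 30.

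The cost is two sentences in Appendix 4, one line for the final call and a few extra pregnancy forms. No visit or procedure is added and no contraception rule changes. The remaining limit is that reports after the final call would still depend on participants coming forward.
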